6.3 Counseling Sessions

All counseling sessions will take place remotely through Zoom, an MGB-approved secure video platform. In both the individual counseling and social network arm, participants will meet with the study nurse with an RA present on weeks 2,6, and 12 (+/- 7 days).

6.3a Counseling Session 1—On Week 2 (+/- 7 days)

The first counseling session will take place two weeks after initial enrollment. Study staff will ensure that only participants who have completed the consent process join the Zoom meeting.

Individual Counseling Arm

Patients in the individual counseling arm will meet individually with the study nurse. The nurse will provide counseling on the basics of blood pressure, taking and adjusting medications, monitoring blood pressure, reducing salt, and being physically active. The patients will then schedule their next session and collect a blood pressure measurement with cuff provided by the study staff under direct supervision by the nurse.

Social Network Arm

At the beginning of this session, the Research Assistant/study staff will confirm that all network-participants have completed the electronic consent process via REDCap.

The study nurse will begin the team-based counseling session in which she will provide counseling on teamwork and the same blood pressure control topics covered with the individual counseling group. The teamwork specific topics will include how networks can work together as a team, communication tips for engaging with one another and spreading positive messages and establishing the roles and responsibilities of each network team member. The team will schedule the following session and the patient will collect a blood pressure measurement with the cuff provided by the study staff under direct supervision by the nurse.

6.3b Counseling Session 2—On Week 6 (+/- 7 days)

The second counseling session will take place six weeks after initial enrollment. Participants in both arms will have received text messages every week in the three weeks between session 1 and session 2. Study staff will ensure that only participants who have completed the consent process join the Zoom meeting.

Individual Counseling Arm

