6.4 End line Study Session—On Week 12 (+/- 7 days)

The third counseling session will take place twelve weeks after initial enrollment. Participants in both arms will have received text messages every week in the five weeks between sessions 2 and 3. Study staff will ensure that only participants who have completed the consent process join the Zoom meeting.

Individual Counseling Arm

Patients in the individual counseling arm will meet for a final time with the study nurse. In this session, the patient will check their blood pressure under direct video observation by the nurse. The nurse will also assess the study's secondary outcomes by taking note of the patient's blood pressure in relation to post-stroke hypertension treatment goal of <130/80 and the patient-reported physical function (based on the NIH PROMIS physical function sub-scale). Participants' social networks will be mapped to assess changes that may have occurred as a result of this study.

Social Network Arm

Patients in the social network arm will meet with their network team and the study nurse for a final time. In this session, the study nurse will first conduct a semi-structured interview with the patient and network members to assess the process and effectiveness of the sessions, as well as their views on their teamwork over the course of the intervention (see "*Interview Guide*" attachment). Prior to the interviews, subjects will be asked to provide verbal consent for audio recording of the interview. Patients will not be forced to participate and may withdraw their consent to participate at any time. Participants will be informed that participation is voluntary and that the interviews are part of the research study. The semi-structured interviews after the will be audio recorded, transcribed by the study team or by Landmark Associates (with whom MGB has a BAA agreement) and analyzed using qualitative software to identify themes using a grounded theory approach.

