All network members will then be asked to leave the Zoom meeting, except for the primary caregiver (if applicable). The patient will collect a final blood pressure measurement under direct supervision of the study nurse, complete the PROMIS physical function scale, and remap their network with the PERSNET instrument to assess any changes that may have occurred as a result of the study. The primary caregiver network member will be asked to complete the caregiver burden scale which will be sent to them via a link in the Zoom chat or via text message.

Outcomes

The primary outcome of the study will be absolute reduction in systolic blood pressure at 3 months. Secondary outcomes will be attainment of a post-stroke hypertension treatment goal and patient-reported physical function. Feasibility measures will also be assessed throughout the intervention. End line caregiver burden will be measured in the social network arm compared to historical control data.

The intervention process evaluation conducted using semi-structured qualitative interviewing during the final session (Social Networks arm) will be analyzed using qualitative software to identify themes using a grounded theory approach. Once the data are analyzed, the investigators will review the findings to consolidate observations into a common set of themes.

Finally, a shortened version of the validated PERSNET utilizing only a subset of the initial questionnaire will be tested for predictive accuracy against the results of the full validated PERSNET scale.

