9.3 Statistical analysis

The primary outcome will be absolute reduction in systolic blood pressure at 3 months. Secondary outcomes will be attainment of a post-stroke hypertension treatment goal of <130/80 and patient-reported physical function (based on the NIH PROMIS physical function sub-scale). These outcomes will be evaluated, for intervention and control patients, on a 10-minute Zoom exit interview with direct observation on video by the study nurse.

Analysis will be conducted using intention-to-treat principles. Evaluation of the primary outcome and physical function secondary outcome will be completed using linear controlling for any differences in baseline variables despite randomization. Logistic regression will be used for attainment of post-stroke hypertension treatment goal of <130/80 controlling for any differences in baseline variables.

For Aim 2, we will assess how a subset of questions in PERSNET predict the set of network members who were engaged in the intervention. We will calculate positive predictive value of the subset questions versus full network survey questions.

10. Monitoring and Quality Assurance

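### PROMIS physical function, a secondary outcome with no baseline measure, is collected at week 12 under conditions that differ by arm

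*Combined protocol and SAP*

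**What the plan says.** Sections 6.4 and 9.3 name patient-reported physical function (PROMIS) as a secondary outcome.

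**Who is on the call.** Section 6.3 has the study nurse deliver the counselling in both arms, with an RA present at weeks 2, 6 and 12. On the control arm it states: "Patients in the individual counseling arm will meet individually with the study nurse".

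**Control arm, week 12 (6.4).** "The nurse will also assess the study's secondary outcomes by taking note of the patient's blood pressure" and, in the same sentence, the PROMIS score. No network member is planned on this call. Only consented participants may join, and section 4.1b draws network subjects solely from patients randomised to the intervention.

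**Social network arm, week 12 (6.4).** The nurse first holds a semi-structured interview with patient and network on the process and effectiveness of the sessions and on their teamwork. Next: "All network members will then be asked to leave the Zoom meeting, except for the primary caregiver (if applicable". The patient then takes a supervised blood pressure reading and is to "complete the PROMIS physical function scale, and remap their network with the PERSNET instrument". The caregiver burden scale "will be sent to them via a link in the Zoom chat or via text message".

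**Both arms (9.3).** The primary and secondary outcomes are evaluated "on a 10-minute Zoom exit interview with direct observation on video by the study nurse".

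**Baseline.** Section 6.1 lists PERSNET, stroke information and the CES-D. Neither that list nor the baseline row of the Data Collection Schedule includes PROMIS.

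**The concern.** PROMIS is a self-report, and self-reports respond to who asks, who is present and what has just been discussed. As written, these conditions differ by arm. Network-arm patients rate their function straight after discussing the benefit of the sessions with the nurse who ran them, and possibly with a member of their coached team still on the call. Control patients do neither. The mode is not standardised either: the nurse assesses the scale in one arm and the patient completes it in the other.

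Randomisation cannot remove a difference that arises at measurement, and neither can the adjustment for baseline variables planned in 9.3. With no baseline PROMIS, the week 12 answer is the whole endpoint, and there is no earlier value for the same patient to set it against. What is at stake is the reading of one secondary comparison: a difference could be real, or could come partly from the setting in which the question was answered.

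**Working it through.** **1. The arms side by side at week 12**

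| Condition when PROMIS is answered | Control arm | Social network arm |
|---|---|---|
| Wording on administration (6.4) | Nurse assesses | Patient completes |
| Nurse observing on video (9.3) | Yes | Yes |
| RA present (6.3) | Yes | Yes |
| Effectiveness interview beforehand (6.4) | No | Yes, led by the nurse |
| Network member planned on the call (6.4) | None | Primary caregiver, if there is one |
| Baseline PROMIS (6.1, Data Collection Schedule) | None | None |

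The nurse and the RA are common to both arms. The arm-dependent features are the preceding interview, the caregiver and the wording on administration. The text describes no masked assessor, no private completion and no matching companion for control patients.

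**2. The plan's own sample size**

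Section 9.2 sizes the trial on systolic pressure: difference 10 mm Hg, SD 13, alpha 0.05, power 80%. Taking alpha as two-sided, which the section does not state:

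n per arm = 2 × (1.960 + 0.842)² × 13² / 10² = 2 × 7.85 × 1.69 = 26.5, rounded up to 27, so 54 in total.

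This matches the plan. It is not in dispute and serves here only to fix the range of 27 (the calculated number) to 30 (the planned enrolment) per arm. The plan gives no SD, target difference or power for PROMIS.

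**3. Illustration of what a reporting shift would do**

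The documents give no size for the shift, so *b* below is an assumption: the average shift across the whole network arm relative to control, in SD units, with no true effect on function.

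Standard error of the difference in SD units: se = √(2/n). This is 0.272 at 27 per arm and 0.258 at 30.

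Probability of a significant result, two-sided 5%, normal approximation: Φ(b/se − 1.96) + Φ(−b/se − 1.96).

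Example, b = 0.2 and n = 27: b/se = 0.735, so Φ(−1.225) + Φ(−2.695) = 0.110 + 0.004 = 0.114.

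| Assumed shift *b* | 27 per arm | 30 per arm |
|---|---|---|
| 0 | 5.0% | 5.0% |
| 0.1 SD | 6.6% | 6.7% |
| 0.2 SD | 11.4% | 12.1% |
| 0.3 SD | 19.7% | 21.3% |

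The t-test gives slightly lower values: 11.1% and 11.9% at 0.2 SD, 19.1% and 20.8% at 0.3 SD. Over both methods the ranges are about 7%, 11-12% and 19-21%.

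The part of *b* due to the caregiver is diluted. It equals the proportion of network-arm patients with a caregiver on the call times the shift among those patients. The plan gives neither. The preceding interview applies across the arm.

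For scale, the difference detectable with 80% power is (1.960 + 0.842) × se, which is 0.76 SD at 27 per arm and 0.72 SD at 30.

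**The case against.** The strongest case against is that this concerns one secondary outcome in a 60-patient pilot powered on blood pressure, and that the bias is conjectural. Much of that case stands:

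- The nurse is common to both arms, so her presence alone does not establish an arm-dependent shift.
- The caregiver stays only where there is one, and the other members leave first, which is a partial safeguard.
- Nothing says that PROMIS is read aloud, so a caregiver on the call need not hear the answers. Rules on joining a Zoom meeting also do not govern who is in the room, in either arm.
- The direction is open: a caregiver could restrain an optimistic answer as easily as encourage one.
- Patients know their own arm, and no collection procedure removes that.
- The RA sits in on sessions in both arms and so knows the allocation. Putting the RA in the nurse's place would not create masking.

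These points limit the size that can be claimed. They do not remove the difference in conditions that 6.4 prescribes.

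A reader might also infer that the nurse collects the end-line PERSNET remap, and that network metrics are therefore biased between arms. The documents do not support this. For controls, 6.4 says only that "social networks will be mapped to assess changes that may have occurred as a result of this study", without naming who does it. In the network arm the patient does the remapping, and the nurse's direct supervision is attached to the blood pressure reading. At baseline, study staff help with the questionnaire (6.1). The remap is not a listed primary or secondary outcome, and 9.3 plans no between-arm comparison of network metrics. Aim 2 concerns the short questionnaire against the full one.

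**Conclusion.** The point holds for PROMIS. As written, a secondary outcome with no baseline value is collected after an effectiveness interview, and possibly with the caregiver on the call, in one arm only. The administration wording also differs. A between-arm PROMIS difference could partly reflect these conditions.

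This rests on reading 6.4 in the order in which it is written and on the nurse knowing the arm. The latter is inferred from her role, since the plan does not mention masking. The false-positive figures depend entirely on the assumed shift and should not be read as an estimate for this trial; at 0.1 SD the effect is slight.

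The primary endpoint and sample size are unaffected. This is a worthwhile, inexpensive improvement and no obstacle to the trial.

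**What to change.** In 6.4:

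- Have patients in both arms self-complete PROMIS through the same REDCap link during the week 12 session, without the nurse or any network member listening. In the network arm, place this before the interview and admit the network members afterwards.
- Keep the RA, who is already present, available for technical problems or to read items aloud.
- After the interview, release the primary caregiver with the other members and send the burden scale by text, a route the plan already allows.
- Keep PERSNET staff-assisted as at baseline, with the caregiver off the call. Moving it to a self-completed link would change its mode between baseline and week 12 and could itself produce apparent network change.

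In 9.3, amend the exit-interview sentence so that nurse video observation applies to the blood pressure reading only.

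The cost is wording in two sections and one REDCap link, with no extra staff, visit or patients. The downside is a small risk of missing or assisted PROMIS forms. Completing the link during the session limits that risk, which matters because only 60 − 54 = 6 patients separate planned enrolment from the calculated number.

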Patients in the individual counseling arm will again meet individually with the study nurse who will review information about taking and adjusting medications, monitoring blood pressure, reducing salt, and being physically active. The patients will also collect a blood pressure measurement with cuff provided by the study staff under direct supervision by the study nurse.

Social Network Arm

Patients in the social network arm will again meet with their network members and the study nurse to review information about teamwork in the context of taking and adjusting medications, monitoring blood pressure, reducing salt, and being physically active that were covered in session 1. The nurse will work with the team for a revised plan, if necessary, to achieve optimal blood pressure by the final session. The patients will also collect a blood pressure measurement with cuff provided by the study staff under direct supervision by the study nurse.

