9.2 Power analysis

This pilot trial will be conducted for 12 months. In that time frame, the study team expects 1126 patients to be eligible across Brigham and Women's Hospital, Massachusetts General Hospital and Spaulding Rehabilitation Hospital (85% of all 1325 ischemic stroke patients given broad inclusion criteria). It is expected that ~20% of the patients will agree to participate based on prior experience of recruitment in this population. This creates a pool of 225 or 19 per month. Thus, the study team can feasibly recruit 60 patients within 4-5 months with buffer for unexpected issues.

Assuming a mean blood pressure of 150 +/- 13 points in the individual counselling arm and an alpha of 0.05, this study will need to enroll a total of 54 patients (i.e., 27 per arm) to have 80% power to detect a 10 mm Hg reduction blood pressure from the social network intervention. Therefore, planned enrollment of 60 should be sufficient power for this study to allow for loss to follow-up.

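### The number of blood pressure readings behind the baseline and week 12 values is not fixed; averaging a preset number would be a cheap gain in precision and would remove discretion

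*Combined protocol and SAP*

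**What the plan says.** The primary outcome is defined in Section 9.3: "The primary outcome will be absolute reduction in systolic blood pressure at 3 months". The same section takes the secondary outcome, reaching the goal of <130/80, from the same video-observed exit visit.

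The measurements behind these outcomes are described as follows.

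- **Baseline (Section 6.1):** one measurement, in the singular, with the study cuff at enrollment. A discharge-day value is also taken from the health record, and patients are told to monitor weekly at home. Neither of these is assigned to an outcome.
- **Week 6 (Section 6.3b):** "The patients will also collect a blood pressure measurement with cuff provided by the study staff". Week 2 is worded much the same.
- **Week 12, social network arm (Section 6.4):** "The patient will collect a final blood pressure measurement under direct supervision of the study nurse".
- **Week 12, individual counseling arm (Section 6.4):** "the patient will check their blood pressure under direct video observation by the nurse".
- **Data Collection Schedule (Section 6.5):** one observed measure per visit.

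No section gives a number of readings, an interval between them, an averaging rule or a rule for choosing the value to analyse.

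**The concern.** Two things are at stake.

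The first is precision. A single cuff reading carries reading-to-reading noise that averaging within the same session would reduce. With 27 analysed patients per arm, that noise goes straight into the standard error of the primary comparison. It also moves patients near 130 mm Hg across the goal line.

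The second is discretion. The nurse who delivers the counseling observes the week 12 reading and, in the individual counseling text, notes the patient's pressure against the goal. That nurse knows the arm, because patients attend either alone or with network members. With no preset count, the nurse could ask for a repeat after a disappointing or borderline value, or choose which of two values to record, and could do so differently in the two arms. A fixed count and a fixed rule close that route.

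**Working it through.** **Inputs from Section 9.2.** "Assuming a mean blood pressure of 150 +/- 13 points in the individual counselling arm and an alpha of 0.05"; "to have 80% power to detect a 10 mm Hg reduction blood pressure from the social network intervention"; and the result, "this study will need to enroll a total of 54 patients (i.e., 27 per arm". Planned enrollment is 60, or 30 per arm. The documents do not say whether the test is two-sided, or whether 13 is the SD of one reading, of an averaged value or of a change.

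**Reproducing the plan's figure.** Two-sided normal approximation:

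n per arm = 2 × 13² × (1.960 + 0.842)² / 10² = 26.5, rounded up to 27, so 54 in total. This matches.

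A one-sided test would need only 21 per arm, so two-sided was evidently meant. The t test, used below, gives 79.2% power at 27 per arm and 83.4% at 30 per arm.

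**Assumption.** The within-visit SD, s, is not in the documents. I take 4, 6 and 8 mm Hg.

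**Case A: the SD of 13 already contains the noise of one reading, and the outcome is the week 12 value.** For the mean of three readings with error correlation r:

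variance = 169 − s² + s²(1 + 2r)/3

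With r = 0 this is 169 − (2/3)s². With r = 0.5 it is 169 − (1/3)s².

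| s | SD, r = 0 | Power, 27 per arm | SD, r = 0.5 | Power, 27 per arm |
|---|---|---|---|---|
| one reading | 13.00 | 79.2% | 13.00 | 79.2% |
| 4 | 12.58 | 81.7% | 12.79 | 80.5% |
| 6 | 12.04 | 85.0% | 12.53 | 82.1% |
| 8 | 11.24 | 89.4% | 12.15 | 84.3% |

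As effective sample size (169 divided by the new variance), the gain is 7%, 17% and 34% with independent errors, and 3%, 8% and 14% with r = 0.5.

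**Case B: the SD of 13 excludes reading noise (independent errors).** One reading has variance 169 + s². The mean of three has variance 169 + s²/3.

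| s | One reading, 27 per arm | Mean of three, 27 per arm | One reading, 30 per arm |
|---|---|---|---|
| 4 | 75.5% | 78.0% | 80.0% |
| 6 | 71.2% | 76.4% | 75.8% |
| 8 | 65.6% | 74.3% | 70.4% |

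Only in this case does a single reading fall materially short of the stated 80% at 27 per arm.

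**Goal classification, systolic part only.** The observed single-reading SD is set at 13, errors are independent, and the observed call of <130 is compared with the patient's noise-free value. Ranges are for s = 4 to 8.

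| Mean SBP | One reading misclassified | Mean of three misclassified |
|---|---|---|
| 150 (planning mean) | 2.9-5.3% | 1.6-2.5% |
| 140 (150 less the 10 mm Hg effect) | 7.3-14.9% | 4.3-8.8% |

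**The case against.** The strongest reply is that the plan never says a value is one reading. A protocol can call a set of readings a measurement, and the individual counseling text at week 12 gives no count at all. That is fair. The single reading is what literal compliance produces, and the firm finding is that the count and the averaging rule are unstated. If several readings are intended, the analysed value is undefined and the same sentence is needed.

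A reader might infer that the trial loses planned power. The documents do not support that. If the SD of 13 comes from single readings, Section 9.2 has already allowed for the noise and its 54 reproduces. Averaging is then a gain.

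A reader might also infer that every blood pressure in the study is a single home-cuff reading. The discharge value comes from the health record, so that is too broad. Nor do the week 2 and week 6 readings feed the primary or goal outcome, so the case for replicates there is weak.

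The misclassification risk can also be made to look larger than it is. A patient with a true systolic pressure of 135 and s = 6 reads below 130 on one reading with probability Φ(−5/6) = 20%, and on the mean of three with probability Φ(−5/(6/√3)) = 7%. But 135 is close to the cut. At 140 the single-reading figure is Φ(−10/6) = 4.8%, and at 150 it is Φ(−20/6) = 0.04%. Diastolic pressure must also be under 80, so 20% is an upper bound on wrongly counting that patient at goal.

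Finally, averaging within a visit does nothing about day-to-day variation, and readings a minute apart may share error. Both limits stand, and the second is why the r = 0.5 figures are shown.

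**Conclusion.** The point holds as a cheap improvement to the design, not as an error in the sample size. The plan fixes neither the number of readings nor the analysed value at the two visits that determine the primary outcome, and taken literally it uses one reading at each.

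The mean of three would add roughly 1 to 10 percentage points of power at 27 per arm. The low end is s = 4 with correlated errors; the high end is s = 8 with independent errors. It would also cut systolic misclassification at 130 by about 40-50%. These sizes rest on the assumed within-visit SD of 4-8 mm Hg, on the SD of 13 containing reading noise, and on the week 12 value as the analysed quantity. If reduction is analysed as a change from baseline, reading noise enters at both ends and the power figures would differ.

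The gain from removing discretion needs none of these assumptions.

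**What to change.** Add to Sections 6.1 and 6.4, with a matching sentence in Section 9.3: at baseline and week 12, in both arms, a fixed number of readings is taken with the study cuff (for example three, about one minute apart); all are recorded; and the mean systolic and mean diastolic values are used for the primary and goal-attainment analyses. Any further reading taken for another reason is recorded but not used in these analyses. Use the same wording for both arms in Section 6.4. In Section 9.2, state what the SD of 13 refers to.

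Two readings, or another preset rule, would also settle the ambiguity, with a smaller gain if fewer are averaged. The cost is a few extra minutes at each of the two visits, which is noticeable against the 10-minute exit interview in Section 9.3, plus a few data fields and one analysis sentence. No new device or staff are needed.
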